5.3. Study Drug Administration

For Parts A, B, and C, subjects will take the study drug (oral capsules of AT-007 or placebo) in the CRU under the supervision of study personnel. Study staff will conduct a hand and mouth check immediately after dose to ensure that the medication has been appropriately swallowed.

For Parts D and E, study drug was oral capsules of AT-007 or placebo. For Part D Extension, both oral capsules and liquid suspensions will be used. Most study drug doses in Parts D, E, and D Extension will be taken on an out-patient basis (i.e., at home). Each subject will be provided with a diary card to record the dates/times for all doses taken at home.

Study drug dose is in mg/kg. For each subject, body weight at screening will be used to determine the amount (mg) of study drug in each dose.

All doses of study drug should be taken under fasting conditions. Subjects should take all doses of study drug in the morning (with water) after overnight fasts of at least 10 hours. Subjects may end their fast at any time ≥ 2 hours after taking the study drug. These conditions are mandatory for doses associated with PK sampling and recommended for all other doses regardless of whether taken at home or in the clinic.

Subjects may drink water ad libitum.

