Male and non-pregnant, non-lactating female adult between the ages of 18 and 65 years, inclusive, with a GALK-deficient Galactosemia diagnosis documented by historical record of either absent or significantly decreased galactokinase (GALK) activity in red blood cells (medical record, enzyme activity report, genetic mutation report, or written communication by health care professional), who have no other significant health problems unrelated to GALK-deficient Galactosemia.

Investigational Product, Dosage and Mode of Administration:

AT-007 (capsules or liquid suspension; single and multiple oral doses): once daily [QD] under fasting conditions for up to 7 days in healthy subjects; up to 27 days in subjects with CG who tolerated a previous single dose (and up to 90 days during an Extension); and up to 27 days in subjects with GALK-deficient Galactosemia who tolerated a previous single dose. Doses between 0.5 and 40 mg/kg, oral, were administered in Part A of the study. Dose levels in subsequent parts of the study are based on the safety, PK, and galactitol (Parts D and E only) results of previous cohorts and/or previous parts of the study. Doses higher than 40 mg/kg may be evaluated if the human maximum observed concentration (C_{max}) and area under the curve (AUC) are substantially lower than the corresponding values calculated in nonclinical experiments and no dose limiting toxicity (DLT) is observed up to and including at the 40 mg/kg dose. If dose escalation above 40 mg/kg is feasible based on the above criteria, these higher doses may be investigated in additional SAD and MAD cohorts in healthy subjects and in subjects with Galactosemia if no AT-007 levels are detected in the CSF collected from the healthy subjects enrolled in Cohort C3. Doses will be rounded according to the available SKU as described in the Pharmacy Manual

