In Parts D, E, and D Extension, the clinical site staff (except for the unblinded pharmacist) and the subjects will be blinded to study treatment. The Sponsor/CRO will not be blinded to study treatment because the relationship between exposure in Parts D, E, and D Extension (subjects with galactosemia) vs. exposure in healthy subjects will need to be evaluated on an ongoing basis to ensure that AT-007 blood levels remain within the limits achieved in Part B. This process will minimize the number of subjects with galactosemia potentially exposed to plasma concentrations of AT-007 not previously tested and shown to be safe in healthy subjects.

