Table 9: PK Parameters of AT-007 During Multiple Dosing in Healthy Subjects (Parts B and C) and Subjects with Galactosemia (MAD Period of Parts D and E and Part D Extension)

PK Parameter	Definition
C_{max}	Maximum concentration, determined directly from individual concentration time data (Day 1 and Day of Last Dose)
T_{max}	Time of the maximum concentration (Day 1 and Day of Last Dose)
λ_z	The observed terminal rate constant; estimated by linear regression through at least 3 data points in the terminal phase of the log concentration-time profile (Day of Last Dose only)
$T_{1/2}$	The observed terminal half-life, calculated as: $T_{1/2} = \frac{\ln(2)}{\lambda_z}$ (Day of Last Dose only)
AUC_{tau}	Area under the concentration-time curve during the 24-hour dosing interval; calculated using the linear trapezoidal rule (Day 1 and Day of Last Dose) Note: If quantifiable data are not observed through 24 h postdose, AUC_{tau} will be estimated using extrapolation (from the time of the last reported concentration to 24 h) and AUC_{last} will also be reported.
AUC_{last}	Area under the concentration-time curve from time-zero to the time of the last quantifiable concentration; calculated using the linear trapezoidal rule (Day of Last Dose; Day 1 if quantifiable data are not observed through 24 h postdose)
AUC_{inf}	Area under the concentration-time curve from time-zero extrapolated to infinity; calculated as: $AUC_{inf} = AUC_{last} + \frac{C_{last}}{\lambda_z}$ (Day of Last Dose only)
$AUC_{Extrap} (\%)$	The percentage of AUC_{inf} based on extrapolation (Day of Last Dose only)
C_{last}	The last quantifiable concentration determined directly from individual concentration-time data (Day 1 and Day of Last Dose)
T_{last}	Time of the last quantifiable concentration (Day 1 and Day of Last Dose)
CL/F	Clearance after extravascular administration, calculated as: CL/F = Dose/ AUC_{tau} (Day X), where Day X = Day of Last Dose and Dose is the actual dose administered (mg/kg x kg). (Day of Last Dose only) Note: CL/F/kg may also be reported
Vz/F	Volume of distribution in the terminal phase, calculated as: Vz/F = (CL/F)/ λ_z (Day of Last Dose only) Note: Vz/F/kg may also be reported

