- j: Samples for clinical safety laboratory tests (hematology, chemistry, coagulation, urinalysis, UACR and UPCR) will be collected under fasting conditions. At the Screening visit only (i.e., only applicable to subjects for whom this visit is required and does not need to be repeated at screening if already done at prescreening), HIV and hepatitis B & C testing will also be done. Hematology, chemistry, and coagulation at the Screening visit (i.e., only applicable to subjects for whom this visit is required) does not need to be repeated if already done at prescreening and prescreening was within 60 days before the first dose of Part D Extension study drug. Clinical safety laboratory tests (hematology, chemistry, coagulation, urinalysis, UACR and UPCR) do not need to be repeated at Day -1 if already done at prescreening or screening and the prescreening/screening visit was done within 60 days before the first dose of Part D Extension study drug.
- k: Serum pregnancy tests will be done at Screening (if applicable), Day -1 (also urine test if serum test cannot be processed immediately), and EOE visits; urine pregnancy tests will be done at all other time points. From Days 1 through 90, pregnancy tests must be done (and the result negative) on dosing days before study drug is administered. A pregnancy test must be performed on Day -1 even if already performed earlier during the screening period.
- m: On Days 1, 2, and 90, study drug will be administered at the clinic. On Days 30 and 60, study drug will be administered during the visit (home health or in-clinic). All other doses of study drug will be taken at home QD with water in the morning (preferably after an overnight fast of ≥ 10 hours with the fast broken ≥ 2 hours after the dose). Study drug administration should be at approximately the same time of day (preferably 8 am) throughout the extension. Drug accountability (including dispensing and/or collecting) will be assessed at all visits during the 90 days of dosing.
- n: On Day 1, a predose (within 60 minutes before the dose) blood sample for PK will be collected. On Days 30, 60, and 90, blood samples for PK will be collected predose (24 hours [± 15 minutes] after the dose taken the day before and within 60 minutes before the dose administered on that day) and at 2, 4, 8, and 12 hours (± 5 minutes for all time points) after the dose. An additional sample will be taken on Day 91 at 24 hour after the Day 90 dose.

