7.3 Multicenter Studies

For Part A, B and C, this is a monocenter study. For Part D, E and D Extension, this is a multicenter study. For the purpose of PK and safety analysis data across sites will be pooled together and presented per dose group.

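### The Part D Extension allows capsule or suspension in one 20 mg/kg group with no formulation factor in the analysis, and its sampling cannot yield the Day 1 PK parameters the plan lists.

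*Protocol*

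**What the plan says.** **Formulation.** Protocol 5.3 gives capsules for the healthy-subject parts ("For Parts A, B, and C, subjects will take the study drug (oral capsules of AT-007 or placebo) in the CRU") and for the first two patient parts ("For Parts D and E, study drug was oral capsules of AT-007 or placebo"). Tables 2 to 6 agree. For the Extension, 5.3 says "For Part D Extension, both oral capsules and liquid suspensions will be used", and Table 7 defines Cohort DE1 as either form at 20 mg/kg, up to 21 active and 7 placebo. Section 3.3.6 bases that dose on Cohort D2, a capsule cohort. The synopsis has a general product description, "AT-007 (capsules or liquid suspension; single and multiple oral doses", which does not place the suspension in any earlier part.

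**Analysis.** Protocol 9.2.1 summarises PK by dose group within each part. SAP 7.10 works by part, cohort and dose level, and allows pooling across all parts at the same dose level for overall dose proportionality. SAP 7.3 says of sites that "data across sites will be pooled together and presented per dose group". SAP Table 3-7 lists DE1 as capsule, SAP 3.1.6 determines compliance by counting capsules, and the SAP 7.4 subgroups (gender, age, BMI, enzyme activity) do not include formulation. SAP section 1 ties the SAP to protocol version 6.0.

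**Sampling.** Appendix F, footnote n: "On Day 1, a predose (within 60 minutes before the dose) blood sample for PK will be collected". The next samples are on Days 30, 60 and 90 (predose, 2, 4, 8 and 12 h), with a 24 h sample on Day 91. Protocol Table 9, whose title covers the Extension, defines Cmax as "Maximum concentration, determined directly from individual concentration time data (Day 1 and Day of Last Dose". It asks for AUCtau on the same two days and, as printed, divides both forms of Rac by Day 1 AUCtau. SAP Table 6-2 repeats this. Protocol 5.2 leaves the Sponsor unblinded because exposure in Parts D, E and the Extension will "need to be evaluated on an ongoing basis to ensure that AT-007 blood levels remain within the limits achieved in Part B".

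**The concern.** Two forms of an oral drug need not deliver the same exposure. The Extension is the longest patient part and has the largest patient cohort, and it is where the second form appears. If formulation is not an analysis variable, the 20 mg/kg concentrations, galactitol changes and adverse event rates may describe a blend of two products. A difference from Cohort D2 could then come from longer treatment or from the form, and the tables could not say which.

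The sampling problem is a plain inconsistency that stands even if the two forms are equivalent: the parameter tables ask for quantities the Extension schedule cannot produce. It also bears on the comparison with Part B in 5.2, because the suspension has no exposure data in these documents and de novo subjects may enter with no PK history of their own.

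**Working it through.** **1. Doses before the first on-drug sample** (protocol 6.8.1 to 6.8.3, Appendix F footnotes a, m and n).
- In clinic: Days 1 and 2 = 2 doses.
- Dispensed for home use: Days 3 to 29 = 29 − 3 + 1 = 27 doses.
- Total before the Day 30 predose sample: 2 + 27 = 29; 29/90 = 32%.
- With the ±2-day window, the visit falls on Day 28 to Day 32: 27/90 = 30% to 31/90 = 34%.

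**2. Day 1 parameters against the schedule.**

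| Part | Day 1 postdose PK samples | Day 1 Cmax and AUCtau obtainable? |
|---|---|---|
| B, C | 0.5 to 12 h, then 24 h | Yes |
| D, E | 0.5 to 48 h | Yes |
| Extension | none | No |

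Without Day 1 AUCtau, Rac has no denominator. Even on Day 30 the first postdose sample is at 2 h, against 0.5 h in Part B, so a comparison of Cmax with Part B stays weaker.

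**3. Where mixing can enter.** SAP 7.10 pools for dose proportionality either on Day 1 or after multiple doses. The Extension has no Day 1 profile, so suspension data could enter only the multiple-dose pool, alongside capsule data from B3, C2 and D2 at 20 mg/kg.

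**4. Possible size of the mixing.** The documents give neither the relative bioavailability F (suspension/capsule) nor the share f on suspension. Assume f = 0.5, a log-normal distribution and a 30% CV within each form.
- Pooled geometric mean relative to capsule = F^f; relative to suspension = F^f / F.
- Log variance = ln(1 + 0.30²) + f(1 − f)(ln F)².

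| Assumed F | Pooled / capsule | Pooled / suspension | Pooled CV |
|---|---|---|---|
| 0.7 | 0.84 | 1.20 | 35% |
| 1.0 | 1.00 | 1.00 | 30% |
| 1.5 | 1.22 | 0.82 | 37% |
| 2.0 | 1.41 | 0.71 | 48% |

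At F = 1 nothing is distorted. Away from 1, the pooled figure describes neither product.

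**5. Would such an F leave the Part B range?** Part B runs from 5 to 40 mg/kg (Table 3). If exposure is proportional to dose, F = 0.7 to 1.5 makes 20 mg/kg suspension equivalent to 20 × 0.7 = 14 up to 20 × 1.5 = 30 mg/kg capsule, inside that range. Mean exposure would reach the 40 mg/kg level only at F = 40/20 = 2. This counts Cohort B4, which the protocol still describes as planned.

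**The case against.** A reader might infer that the safeguard in 5.2 fails for every Extension subject through 29 doses, or that subjects are dosed at home outside tested exposure. The documents do not support either reading. Section 5.2 describes an ongoing process meant to minimise the number of subjects exposed to untested concentrations; it does not promise each subject a check before Day 30. Section 3.1 expects staggered enrolment, so early Day 30 results can inform later subjects. Capsule exposure at 20 mg/kg was already studied in B3, C2 and D2. Plausible ratios stay inside the Part B range under the assumptions in the working. What stands is narrower: the first suspension subjects have neither their own level nor anyone else's in these documents.

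A reader might also take SAP 7.3 as a decision to pool formulations. It is about sites. No sentence says the forms will be combined; that follows from the absence of a formulation factor. The SAP follows protocol 6.0, with a capsule-only Extension of at most 16 subjects, and the protocol requires it to be final only before database lock. This is best read as a version lag. By-subject listings of dosing, concentrations and PK parameters would allow separation, but only if formulation is recorded. Protocol 5.4 already covers suspension compliance, and the SAP compliance formula (doses taken over doses planned) suits either form.

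Suspension PK may exist in documents not seen here, and Table 9 is a generic table whose Day 1 entries could simply be marked not applicable. Both points are fair. Neither removes the need to update the SAP and reconcile the tables.

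**Conclusion.** The point holds as two documentation and analysis gaps that should be closed before the Extension is analysed. First, two products share one 20 mg/kg group with nothing in the plan to separate them. The effect is zero if the forms are equivalent. Under the assumed half-and-half split, the pooled geometric mean would be 16% below capsule at F = 0.7 and 22% above at F = 1.5. These figures are illustrations: neither F nor the share on suspension is documented, so it cannot be said that all 21 active subjects are affected. Second, Day 1 Cmax, Day 1 AUCtau and Rac are listed for the Extension and cannot be obtained there. This rests on no assumption. The comparison with Part B cannot use a subject's own on-drug level until Day 30, which matters mainly for the first suspension subjects. No exposure difference and no breach of the Part B limits is shown.

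**What to change.** **(a) Formulation.** Record formulation per subject as an analysis variable. Within 20 mg/kg, present Extension AT-007 concentrations and PK parameters, galactitol and TEAEs by formulation. Exclude suspension data from the cross-part dose-proportionality pooling in SAP 7.10 unless the two forms are shown to be comparable. Add the suspension to SAP Table 3-7 and to the capsule-count sentence in SAP 3.1.6. The cost is one variable and some split tables. The downside is smaller groups, which is tolerable because the summaries are descriptive.

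**(b) Day 1 parameters.** Mark Day 1 Cmax, Day 1 AUCtau and Rac as not applicable to the Extension in protocol Table 9 and SAP Table 6-2. Make 5.2 match the sampling by stating that the Extension comparison with Part B starts at Day 30. This costs text changes only.

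**Optional, for the sponsor to weigh.** Day 1 postdose samples in suspension subjects, at the 2, 4, 8, 12 and 24 h points used around the Day 90 dose, would give the missing parameters. That is five extra draws per subject. Appendix F footnote o ties biomarker sampling to the PK times, so it would trigger biomarker draws as well unless amended. The hotel option in 6.8 complicates collection, and nothing in the documents shows that results would return before home dosing begins. It is not a required part of the fix.

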5.4. Treatment Compliance

Treatment compliance is assured during Parts A, B, and C and for in-clinic doses during Parts D, E, and D Extension because subjects will take the study drug in the CRU under supervision by the study center staff.

During Parts D, E, and D Extension study drug will be dispensed and collected periodically because subjects will be taking most doses at home. Treatment compliance will be determined by counting the capsules (or otherwise measuring study drug dispensed to Part D Extension subjects taking the liquid suspension) dispensed and collected at each of these visits and by reviewing subjects' study drug diary cards.

5.5. Fasting/Meals/Beverages

During the stays in the CRU, subjects' meals and beverages will adhere to the study restrictions ([Section 4.6](#)). In addition, subjects will be fasted overnight for at least 10 hours before study drug administration on the mornings of study drug dosing days and the fast will be broken at ≥ 2 hours after the dose.

During the out-patient periods of the study, it is recommended that subjects take the study drug under the same fasting conditions. Subjects/caregivers will be instructed to have the subject fast overnight for at least 10 hours before study drug administration on the mornings of study drug dosing days and break the fast at ≥ 2 hours after the dose. Subjects/caregivers will also be instructed to adhere to the study restrictions ([Section 4.6](#)) and report any lapses.

Throughout the study, healthy subjects will maintain their normal/usual diet.

Throughout the study, subjects with CG or GALK-deficient Galactosemia will maintain their normal/usual galactose-restricted diet that eliminates sources of galactose from dairy products but permits minimal dietary intake of galactose from non-dairy products.

Subjects will be encouraged to drink water ad libitum.

6. STUDY PROCEDURES BY VISIT

The Schedules of Assessments for Parts A, B, C, D, E, and D Extension of the study are provided in [Appendix A](#), [Appendix B](#), [Appendix C](#), [Appendix D](#), [Appendix E](#), and [Appendix F](#), respectively.

The Screening Visit and EOS (or EOE) Visit can be done at any time of day, but the subject should arrive in a fasted state after fasting for at least 10 hours.

For the Check-in Visits for Parts A, B, C, and D Extension, the subject should arrive at the CRU around 11 am. For the Check-in Visits for Parts D and E, the subject should arrive at the CRU in the morning in a fasted state after fasting for at least 10 hours. The subject should not take study drug before arriving at the CRU because study drug will be administered at the visit as needed.

For the arrival times and conditions of all other visits, please refer to the Schedules of Assessments for Parts A, B, C, D, E, and D Extension ([Appendix A](#), [Appendix B](#), [Appendix C](#), [Appendix D](#), [Appendix E](#), and [Appendix F](#), respectively). If nothing is stated explicitly regarding arrival time, whether the subject should be in a fasted state, and/or whether the subject should have taken study drug or not, then assume that the subject can arrive at any time, fasted vs fed does not matter, and/or the subject should have taken study drug at home (if during a dosing period).

For each visit, the visit procedures are listed in the approximate order in which they should be performed. However, the order of some procedures may be changed for practical reasons (when the subject arrives relative to the planned time of dosing and when the subject is able to produce a urine sample) as long as the procedures are done within the required timeframe and under the required conditions (fasting vs non-fasting and/or before vs after the dose). For example, fasting blood and urine samples for clinical safety laboratories are usually written as occurring after the dose because of the importance of the timing of the dose; however, the fasting safety laboratory samples may be taken at any time before the subject breaks the fast after the dose.

Acceptable windows for visit procedures are provided in the footnotes in the Schedules of Assessments. In case of overlapping time points, meeting the nominal time point for study drug dosing and collecting blood samples for PK and/or biomarkers take priority over meeting the nominal time point ECGs and vital signs which take priority over meeting the nominal time point for physical examinations and collecting samples for clinical safety laboratory tests.

NOTE: If extenuating circumstances (i.e., COVID-19 pandemic) make clinic visits inadvisable/impractical/unwanted for subjects, study visits will be done as home visits by a visiting nurse with some equipment/supplies sent to the subjects' home for the duration of their study participation. The details regarding these home health visits are described in a separate document entitled "Work Instructions for Conduct of Home Health Protocol Visit(s) during COVID-19 Pandemic".

6.1. Prescreening Period (De novo Part D Extension Subjects Only)

Prescreening can be done at any time during a home health visit (in-clinic visit also permitted). The purpose of prescreening is to identify subjects who may be interested in and qualify for the study. A prescreening ICF must be completed before any study-specific prescreening procedure is conducted.

Prescreening is optional. Some subjects may do the prescreening activities as part of screening.

Prescreening activities may include the following:

- Collect blood sample for assessment of GALT activity in RBCs and GALT gene analysis
- Collect urine sample (spot collection) for analysis of galactitol
- Collect fasting blood sample(s) for clinical laboratory testing (hematology, coagulation, and chemistry) and serology testing (screening for HIV, hepatitis B, and hepatitis C)
- Measure body weight
- Measure height
- Obtainment of medical history only for documented diagnosis of Galactosemia, if available

6.2. Screening Period (Days -28 through -1 for Parts A, B, and C and Days -40 through -1 for Parts D and E, and Days -60 through -1 for Part D Extension)

The screening visit must occur within 28 days before the first dose of study drug for Parts A, B, and C; within 40 days before the first dose of study drug for Parts D and E; and within 60 days before the first dose of study drug for Part D Extension.

The Part D Extension screening visit is only applicable to the following subjects:

- De novo subjects
- Subjects whose last visit in Part D was >60 days before Day 1 in Part D Extension

Part D Extension subjects who previously participated in Part D and had a last Part D visit within 60 days before Day 1 of the extension do not need a screening visit for the extension.

Subjects will be evaluated at the screening visit to determine their eligibility to enroll in the study. The following procedures will be done at screening (home health visit or in-clinic visit):

- Obtain signed informed consent from the subject and from the subject's caregiver/LAR (if applicable)
The informed consent documents will be discussed with each potential subject and caregiver/LAR (if applicable), and each potential subject (and caregiver/LAR if applicable) will sign the informed consent form(s), as appropriate, for the study prior to any study-specific procedures being performed.
- Review inclusion/exclusion criteria
- Obtain medical history (including current medication)
- Obtain demographic data (not necessary for Part D subjects being re-screened for Part D Extension)

- Perform physical examination including height (unless already taken at prescreening) and weight
- Measure vital signs
- Conduct 12-lead ECG
- Collect fasting blood sample(s) for clinical laboratory testing (hematology, coagulation and biochemistry); serology testing (screening for HIV, hepatitis B, and hepatitis C); and, for female subjects of childbearing potential only, serum pregnancy test (also FSH test for female subjects claiming postmenopausal status) (Note: The clinical laboratory testing and serology testing do not need to be repeated if already done at prescreening and prescreening was within 60 days before the first dose of study drug in Part D Extension.)
- Collect fasting urine sample for urinalysis, drugs of abuse screen (also cotinine screen for subjects in Parts A, B, and C only), and for the following urinary markers of renal function: Urine protein-to-creatinine ratio (UPCR), urine albumin-to- creatinine ratio (UACR).

For Parts D, E, and D Extension only, the following procedures will be done in addition to the ones listed above:

- Collect blood sample for assessment of GALT or GALK activity in red blood cells and GALT or GALK gene analysis (GALT for Parts D and D Extension and GALK for Part E) (if not already done during prescreening)
- Collect blood sample for assessment of aldose reductase activity
- Collect blood sample for analysis of biomarkers of galactose metabolism including galactose, galactitol, and galactose-1-p
- Collect urine sample (spot collection) for analysis of galactitol (if not already done during prescreening)

Note: For Part D Extension subjects who were previously screened for Part D but had the last Part D visit >60 days before Day 1 in the extension, GALT and aldose reductase activity assessments do not need to be repeated.

Subjects who are taking any disallowed medication(s) (see [Section 4.1.2](#), [Section 4.2.2](#), and [Section 4.6](#)) but otherwise eligible for the study may washout their disallowed medications (washout of at least 5 half-lives of the disallowed medication with the longest half-life). After the washout period, they may be rescreened.

Eligible subjects will be contacted to inform them of their eligibility and schedule the start of study drug dosing for those wishing to continue in the study. Subjects (and caregivers if applicable for Part D Extension) in Parts A, B, C, and D Extension will be instructed to arrive at the CRU at approximately 11 am on the day before the scheduled first dose of study drug. Subjects/Caregivers in Parts D and E will be instructed to arrive at the CRU in the morning on the day before the scheduled first dose of study drug (i.e., approximately 24 hours before the first dose).

